#### Appendix B RECEDE recruitment and assessments process

Plan 1 – Recruiting in Clinic

**NOTE:** Questionnaires are only being completed at sponsor site (UHCW).

Appendix B Figure 1 RECEDE clinic recruitment and assessment flow chart.
## Plan 2 – Recruiting Remotely

**NOTE:** Questionnaires are only being completed at sponsor site (UHCW).

Appendix B Figure 2 RECEDE remote recruitment and assessment flow chart.

Appendix C Participant referral pathways

#### Patient Pathway Before COVID-19

\*values are estimates and will vary regionally based on demand and available capacity

Appendix C Figure 3. The changes caused by COVID 19 to patient referral pathways for colonoscopy

# Appendix D Volatile Organic Compounds (VOC) Sampling

VOCs are detected by applying a solid-phase micro extraction (SPME) technique to the urine samples. SPME is a technique which is established as a means for preconcentrating samples for analysis by gas chromatography and has been adapted for this study to capture and present VOCS to a gas sensor array used as a detector. The technique is applicable for gas and liquid samples. Special absorptive or adsorptive 'sorptive' materials are used to extract analytes of interest by capturing them in their matrices. The sorptive materials are then heated to a suitable temperature to cause the analyte to desorb from the coating and pass directly into the analytical part of the instrument. In this case proprietary SPME polymer tabs manufactured by Sensam Ltd are used to capture urine VOCs.

- 1. Specimen bottles with frozen urine samples are placed in water bath, set to 25C, for 1 hour.
- 2. Bottle with thawed samples is shaken briefly to mix the contents.
- 3. Sample ID is written two sealable plastic bags with suffixes a and b respectively.
- 4. A thawed sample is transferred to a larger sample bottle (big enough to accommodate SensAm Tabs).
- 5. A lid with two slots is screwed onto the larger sample bottle.
- 6. Two SensAm Tabs are removed from the packaging and inserted into the slots in the lid of the bigger sample bottle.
- 7. Tabs are left in the head space above the sample for 5 minutes.
- 8. After 5 minutes Tabs are removed from the slot in the lid, placed it into the sealable bags, labelled in step 3 above, which are then sealed.
- 9. Sample and the bottles are disposed of according to appropriate procedures for the disposal of such materials and items.
- 10. Sealed bags with exposed Tabs are taken to SensAm's instrument.

## **Exposed Tabs Processing**

When the Sensor Tabs are inserted in to the SensAm device for VOCs analysis, they are then automatically heated in the device to 120°C to desorb captured VOCs. Responses from the array of gas sensors to the desorbed vapours are captured over a period of 180 seconds, digitized and stored.

- 1. When SensAm's instrument shows "Ready, Insert Sensor Tab" message, one exposed tab is removed from the sealed plastic bag.
- 3. The data logging file is named after the label on the bag, including the suffix.
- 3. The Tab is inserted into the input port of the instrument.
- 4. Tab processing is started by touching the screen when invited to do so.

IRAS 282247\_RECEDE protocol\_v2.2\_11.02.2022 Page **40** of **50** 

- 5. When instrument indicates that the Tab processing is completed, the file with the logged data is saved.
- 6. The used Tab is removed from the input port of the instrument when instrument issues an instruction do so and discarded in the appropriate waste bin.
- 7. Steps 1 to 7 are repeated until all exposed Tabs are processed.

#### **Data Analysis**

- 1. Each logged data file is transferred to the SENSAMSNIFFER program.
- 2. Appropriate data base containing key points from captured profiles is generated.
- 3. Analysis of the data base is performed, as required, using the SENSAMSNIFFER program.

## Appendix D Figure 4 Data processing protocol.

Appendix D Figure 4 shows an outline of the data processing protocol. The portion of the gas sensor response corresponding to the detection of desorbed volatiles from an individual sample is extracted and averaged to produce n=5 samples straddling the response profile. For each patient sample, databases of the patterns are created, and these form the basis for further data processing. To visualise the data from all the samples that are processed, the method of principal components analysis (PCA) is used to provide an unbiased means of observing clusters or patterns when amalgamating samples from a patient population and a control population.

To discriminate between different classes of data a neural network based on radial basis functions is employed. Radial basis function networks (RBFN) are a variant of three-layer feedforward neural networks. They contain an input layer, a hidden layer and an output layer where the transfer function in the hidden layer is called a radial basis function (RBF). To each individual pattern in the databases a class

IRAS 282247\_RECEDE protocol\_v2.2\_11.02.2022 Page **41** of **50** 

name is assigned. The neural network is trained against a subset of sample patterns and a bootstrap method used for validation and testing the prediction accuracy of the neural network against previously unseen samples. The output nodes of the neural network are scaled to provide an output scaled between 0 to 1 representing the probability of an input sample pattern belonging to a certain class.

Positive predictive value is the proportion of positive results that are true positives (i.e. have the target condition) whereas negative predictive value is the proportion of negative results that are true negatives (i.e. do not have the target condition). This approach usually requires the creation of a cut-off point from continuous data and depending on the cut-off selected, the sensitivity and specificity of a test will vary. If the cut-off is selected so that the sensitivity increases, the specificity will decrease. ROC curves are a way of graphically displaying true positives versus false-positives across a range of cut-offs and of selecting the optimal cut-off for clinical use to be selected. To generate Receiver Operating Curves (ROC ), the neural network is trained on a series of test cases versus controls, and ROC are generated for each of the test cases from the outputs of the neural network when tested against previously unseen patterns, using established algorithms. The ROC curves are analysed to determine appropriate thresholds to optimise sensitivity and selectivity of the VOC analysis tests. These studies address how well the VOC test identifies the target condition of interest. Appendix D Table 2 below shows the data generated by the neural network and ROC analysis.

Result	Disease Present	Disease Absent	Total
	True Positive (TP)	False Positive (FP)	TP+FP
	False Negative (FN)	True Negative (TN)	TN+FN
Total	TP+FN	TN+FP	
Sensitivity	TP/(TP+FN)		
Specificity	TN/(TN+FP)		
Positive predictive value (PPV)	TP/(TP+FP)		
Negative predictive value (NPV)	TN/(TN+FN)		
Positive likelihood ratio	Sensitivity/(1-		
(LR+)	specificity)		
Negative likelihood	(1-		

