#### 8 STATISTICS AND DATA ANALYSIS

8.1 Sample size calculation

To replace colonoscopy and CTC the new testing strategy requires very high sensitivity to avoid false negative results and missed disease. False positive results are also undesirable, but these participants would simply follow the colonoscopy testing pathway that all participants follow currently. Therefore, the sample size calculations are based on achieving acceptable sensitivity. There are some data on the utility of FIT alone and urine VOC alone in the detection of SBD(6, 10, 37). Our recent study (n=562) is the only published study that evaluated the combination of both FIT and urine VOC for the detection of colon cancer, which was 97% (95% CI: 90 to 100), similar to that for colonoscopy(6). The sensitivity of FIT alone in detecting IBD is 0.85, with the combined accuracy of FIT and VOC unknown. On the basis of these previous studies, and the necessity for high sensitivity to replace colonoscopy, we assumed that the sensitivity (Se) of the FIT and urine VOC tests to detect SBD would be at least 0.97 which is very near 1.0. The confidence interval for such high sensitivity has to be adjusted such that the interval does not exceed 1.0. One recommended method is to use the Zhou-Li method as described in equations 4.5 to

replaced by Se. Assuming that the sensitivity of FIT and VOC to be at least 97% then for Se = 0.97 and a 95% CI width of 0.05 (ensuring a high precision around the sensitivity estimate) the required number of participants with SBD is 200. Further assuming that the prevalence of SBD in the population with bowel symptoms is 19% (likely underestimate), then 1053 participants are required. Based on previous study(6) about 55% of the participants would return both stool and urine samples and sufficient for FIT and VOC analyses. Thus, the total sample size required is 1,915.

This strategy is robust to changes in the underlying assumptions of test accuracy. Confidence intervals for sensitivity for different observed sensitivity for 150, 200 and 250 cases of SBD are shown in Figure 5(a). For the target sensitivity of 0.97, the width of the confidence interval is 0.05 with 200 SBD participants, with narrower and wider confidence interval limits, when the observed sensitivity is above and below this value, respectively (Figure 5(b)).

Figure 5 Confidence intervals for different estimates of sensitivity for 150, 200 and 250 cases of SBD.

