The first two parts of the model will be run for each of the conditions classified as SBD (i.e. colorectal cancer, colorectal adenomas and inflammatory bowel disease).

Calculations will consider all key costs and consequences, including the costs and 'disutility' associated with having a colonoscopy or CTC. Model input will be drawn from relevant sources, including the RECEDE study and the available literature. For example, parameters related to the diagnostic characteristics of the compared options—which will be a key input in the first part of the model and a crucial parameter for the overall analysis—will be collected directly from RECEDE (we will model the accuracy at the thresholds pre-specified in the primary outcome, and the optimal thresholds from the exploratory analysis). Further information for the economic model, such as estimates of the rate of adverse outcomes associated with colonoscopies (e.g. bowel perforation and bleeding) or CTCs, preference-based health-related quality of life (utility) values and primary and secondary care resource use for the diagnostic part of the model will be collected from a sample of 370 RECEDE participants (20% of the total intended sample) recruited at UHCW. The questionnaires will continue to be administered until 370 participants have completed all five of their questionnaires.

In planning the study, we considered carefully whether collecting information on the 'disutility' of colonoscopy from patients at one site would introduce any unanticipated bias. We believe that the nature of the data we are interested in (impact of colonoscopy or CTC on patient's quality of life over the short time period before and after the procedure) and the fact that colonoscopy and CTC procedures and the preparation stage preceding them is well defined and standardised across NHS settings, makes it unlikely that single site data collection will results in any unanticipated bias or unrepresentativeness. Given this, and the fact that other sites indicated that further data collection (quality of life questionnaires) might be a barrier to recruitment, we felt that collecting data from a single site is sensible and justifiable.

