Appendix D Table 2 Data generated by the neural network and ROC analysis

ratio (LR-)	sensitivity)/specificity	

- (a) Sensitivity, specificity, predictive values and likelihood ratios (LRs) are all different ways of expressing test performance.
- (b) Receiver operating characteristic (ROC) curves compare sensitivity versus specificity across a range of values for the ability to predict a dichotomous outcome. Area under the ROC curve is another measure of test performance.
- (c) All of these parameters are not intrinsic to the test and are determined by the clinical context in which the test is employed.
- (d) High sensitivity corresponds to high negative predictive value and is the ideal property of a "rule-out" test.
- (e) High specificity corresponds to high positive predictive value and is the ideal property of a "rulein" test.

From previous work [6] it has been shown that the use of FIT alone for CRC detection revealed a sensitivity of 0.80 [95% confidence interval (CI) 0.66– 0.93] and specificity of 0.93 (95%: CI 0.91–0.95). The use of urinary VOC's for the detection of CRC gave a sensitivity of 0.63 (95% CI: 0.46–0.79) and specificity of 0.63 (95% CI: 0.59–0.67). The AUC was 0.67 (95% CI: 0.57–0.77) and the NPV was 0.96 (95% CI: 0.94–0.98). For high-risk adenoma and all adenomas, using urinary VOCs the sensitivity was 0.93 (95% CI: 0.81–1.0) and 0.91 (95% CI: 0.85–0.97), respectively, with specificity of 0.16 (95% CI: 0.13–0.20) and 0.15 (95% CI: 0.12–0.19), respectively. These data give a guide for fixing a sensitivity threshold for the VOC analysis which we propose as a probability of **0.63** on the basis of the above data. This would be refined as the study progresses to optimise the sensitivity and selectivity for the VOC analysis and to examine the effects of combining FIT plus VOC analysis.

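### Appendix D conflicts with the fixed primary VOC cut-off and leaves the network's training source and split unit open, so the primary accuracy could be optimistic

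*Protocol*

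**What the plan says.** **Classifier.** Appendix D (data processing, Figure 4) describes a radial basis function network. A class name is attached to each pattern, and "The neural network is trained against a subset of sample patterns and a bootstrap method used for validation and testing the prediction accuracy". The output is scaled from 0 to 1 as a class probability. Section 8.2.2 turns that output into the primary VOC result (positive above 0.63) and combines it with FIT by an OR rule.

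**Patterns per person.** Two tabs are exposed to each urine sample, and the sensor response "is extracted and averaged to produce n=5 samples straddling the response profile".

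**Test unit.** The sentence on the bootstrap goes on to speak of unseen samples. The later text on ROC curves has the network assessed "when tested against previously unseen patterns, using established algorithms".

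**Cut-off.** Section 8.2.2 fixes it at 0.63. Section 8.3 agrees: "we will model the accuracy at the thresholds pre-specified in the primary outcome". Below its Table 2, Appendix D only proposes 0.63 and adds: "This would be refined as the study progresses to optimise the sensitivity and selectivity for the VOC analysis". Section 7.4 and Appendix D also use ROC curves to set thresholds.

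**Numbers.** Section 8.1 plans "for Se = 0.97 and a 95% CI width of 0.05", and concludes that "the required number of participants with SBD is 200". Section 8.2.2 drops only participants with a missing index test or reference standard. Section 8.2.3 admits overestimated accuracy, but only for the thresholds derived in the secondary analysis.

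**The concern.** A classifier assessed on people who helped to train it, or at a cut-off adjusted to their results, looks better than it is. The plan gives two routes to this in the primary analysis.

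First, no external training set and no locked network are described, and no participants are reserved for training. The apparent source is therefore RECEDE itself, and the same people also enter the primary 2x2 tables. If several patterns of one person are divided between training and test, the network can recognise the person rather than the disease.

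Second, a cut-off that is refined during the study is no longer pre-specified.

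Either route would raise the reported sensitivity, specificity, PPV and NPV of VOC and of FIT plus VOC. The economic model takes these estimates as inputs.

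**Working it through.** **1. The plan's own figures.** The Zhou-Li formula is not legible in the available text, so the Wilson interval is used, with z = 1.96:

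width = 2z·√[p(1−p)/n + z²/(4n²)] / (1 + z²/n)

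At p = 0.97 and n = 200: 3.92 × √(0.0001455 + 0.0000240) / 1.0192 = 0.050. Other intervals at n = 200 give 0.047 (Wald), 0.048 (Jeffreys), 0.052 (logit) and 0.053 (Clopper-Pearson). Then 200/0.19 = 1052.6, so 1,053, and 1053/0.55 = 1914.5, so 1,915. Section 8.1 is reproduced. It contains no allowance for training cases.

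**2. The passages side by side.**

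| Item | One place | Another place |
|---|---|---|
| VOC cut-off | 8.2.2 and 8.3: fixed at 0.63, pre-specified | Appendix D: 0.63 proposed, then refined during the study |
| Test unit | Appendix D, bootstrap sentence: samples | Appendix D, ROC text: patterns |
| Training data | Appendix D: a subset | 8.1 and 8.2.2: nobody set aside |

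The word samples does not settle the unit, because the same paragraph also uses it for the five averaged points. One response gives 5 patterns. If each of the two tabs gives one response, a urine sample gives 2 × 5 = 10.

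**3. Effect of the split unit.** Simulation with no VOC signal (true AUC 0.50): radial basis function network, 600 participants, 70% used for training, predictions averaged by participant. The within-person correlation is not in the protocol and is assumed.

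| Within-person correlation | Pattern split, 5 patterns | Pattern split, 10 patterns | Participant split |
|---|---|---|---|
| 0.5 | 0.59 | 0.62 | 0.47–0.48 |
| 0.8 | 0.75 | 0.82 | 0.47–0.50 |
| 0.95 | 0.87 | 0.92 | 0.49–0.50 |

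At a correlation of 0.8 or more, a pattern split passes the AUC criterion of 0.63 in Section 7.4 with no signal at all. In one run of a bootstrap by participant (5 patterns, correlation 0.8), every participant received an out-of-bag prediction and the AUC was 0.52.

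**4. Where VOC decides the combined result.** Section 1.9 (Dual Testing) gives 37% of SBD as FIT negative: 0.37 × 200 = 74 cases. Under the OR rule, with v the VOC sensitivity in these cases, combined sensitivity = 0.63 + 0.37v. For 0.97, v = 0.34/0.37 = 0.919. For comparison, v = 0.80 gives 0.926 and v = 0.63 gives 0.863. Optimism in v therefore passes into the primary sensitivity at a rate of 0.37.

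**5. If training participants were instead held out once.** The protocol states no such hold-out and no fraction, so a range is assumed (Wilson width at 0.97):

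| Share used for training | SBD cases left | Width |
|---|---|---|
| 20% | 160 | 0.057 |
| 30% | 140 | 0.061 |
| 50% | 100 | 0.074 |
| 70% | 60 | 0.101 |
| 80% | 40 | 0.130 |

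With out-of-bag or out-of-fold prediction by participant, all 200 cases count and the width stays near 0.05, ignoring the extra variance from model fitting.

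**The case against.** Several points on the other side have force.

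- **Split unit.** A reader might infer that the split is by pattern. The protocol does not establish that. The bootstrap sentence refers to unseen samples, and nearby text uses sample for a patient's urine. What stands is that the two statements differ and neither keeps a person's patterns together.
- **Training source.** Appendix D speaks of patient and control populations, and RECEDE has no control arm, so the text may be a generic account of the laboratory method. Training on RECEDE is an inference. It is a strong one: the extraction technique is said to be adapted for this study, Section 7.4 sets thresholds by ROC analysis, and refinement is to happen during the study.
- **Cut-off.** A reader might infer a settled plan to tune the primary cut-off. Section 8.2.2 fixes it, Section 2.1 calls threshold optimisation exploratory, and Section 8.3 keeps the two sets of thresholds apart. The Appendix D sentence goes on to the combination of FIT and VOC, which fits the secondary work in 8.2.3. What remains is a contradiction, because that sentence carries no such limit.
- **SAP.** Fold grouping is ordinary SAP content, and the SAP is not shown. But the protocol already makes conflicting statements. Its only condition, at the end of 8.2.3, is that the SAP be signed off before the final analyses, which would not prevent earlier tuning against reference results.
- **Measure.** AUC is not the primary measure, and the simulation does not quantify bias in the combined sensitivity. This stands.

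**Conclusion.** The concern holds as a contradiction and an unguarded route to optimistic primary accuracy. It is not proof that the estimate will be biased.

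If the split is by pattern, a VOC test without signal could show an AUC of about 0.59 to 0.92. The range depends on the assumed within-person correlation (0.5 to 0.95) and number of patterns (5 or 10). For the combined sensitivity the exposure is limited to about 74 of 200 SBD cases, if the 37% FIT-negative share carries over to this study.

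It is tempting to conclude that the primary result must be either optimistic or based on far fewer than 200 SBD cases. The protocol does not support that. It names a bootstrap, and out-of-bag prediction by participant keeps every case. The widths of 0.057 to 0.130 apply only to a single hold-out, which it does not state. Section 8.1 is arithmetically sound.

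The point still needs correction before reference results are linked for evaluation, because as written a reader could not tell how far the primary estimate is free of optimism.

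**What to change.** Reconcile Sections 7.4, 8.2.2 and 8.3 with Appendix D, and state the following:

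1. The source of the training data: RECEDE, or a named external set with a network locked beforehand.
2. All patterns and both tabs of a participant stay on the same side of every split or bootstrap draw.
3. The primary 2x2 tables use one prediction per participant, either out-of-fold or out-of-bag by participant, or from the externally locked network. All of the roughly 200 SBD cases then count.
4. The primary cut-off stays at the 0.63 pre-specified in 8.2.2 and is not refitted within folds.
5. The pipeline specification (features, network, tuning procedure, splitting scheme) is locked before reference results are linked for accuracy evaluation. After that, reference labels are used only within training folds.
6. The Appendix D sentence on refinement is confined to the secondary and exploratory threshold work in 8.2.3, where the overestimate is already acknowledged.

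The cost is protocol and SAP wording and more computing. Reported accuracy may look less favourable. No further participants are needed, and N stays 1,915.

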Appendix D Table 2 Data generated by the neural network and ROC analysis

ratio (LR-)	sensitivity)/specificity	

- (a) Sensitivity, specificity, predictive values and likelihood ratios (LRs) are all different ways of expressing test performance.
- (b) Receiver operating characteristic (ROC) curves compare sensitivity versus specificity across a range of values for the ability to predict a dichotomous outcome. Area under the ROC curve is another measure of test performance.
- (c) All of these parameters are not intrinsic to the test and are determined by the clinical context in which the test is employed.
- (d) High sensitivity corresponds to high negative predictive value and is the ideal property of a "rule-out" test.
- (e) High specificity corresponds to high positive predictive value and is the ideal property of a "rulein" test.

From previous work [6] it has been shown that the use of FIT alone for CRC detection revealed a sensitivity of 0.80 [95% confidence interval (CI) 0.66– 0.93] and specificity of 0.93 (95%: CI 0.91–0.95). The use of urinary VOC's for the detection of CRC gave a sensitivity of 0.63 (95% CI: 0.46–0.79) and specificity of 0.63 (95% CI: 0.59–0.67). The AUC was 0.67 (95% CI: 0.57–0.77) and the NPV was 0.96 (95% CI: 0.94–0.98). For high-risk adenoma and all adenomas, using urinary VOCs the sensitivity was 0.93 (95% CI: 0.81–1.0) and 0.91 (95% CI: 0.85–0.97), respectively, with specificity of 0.16 (95% CI: 0.13–0.20) and 0.15 (95% CI: 0.12–0.19), respectively. These data give a guide for fixing a sensitivity threshold for the VOC analysis which we propose as a probability of **0.63** on the basis of the above data. This would be refined as the study progresses to optimise the sensitivity and selectivity for the VOC analysis and to examine the effects of combining FIT plus VOC analysis.

An assignment of pre-test probability is a major factor influencing any decision to undertake a diagnostic test or not and it presupposes that there is diagnostic uncertainty that is the reason for this study. Related to this are the concepts of test and treatment thresholds. If the probability of a condition is very unlikely (i.e. below the test threshold), it can be eliminated from the differential diagnosis. If the probability is sufficiently high for treatment to be initiated (above the treatment threshold), then testing is not really required. Where the probability lies between the two thresholds, further diagnostic testing is indicated. Where the thresholds are set depends upon the clinical context and clinician preference which are all part of the RECEDE study where the combination of FIT and VOC measurements would tend to enhance the certainty of a diagnosis.

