The urinary volatiles will be analysed in Manchester using "electronic nose" techniques using an array of gas sensors coupled with an appropriate polymeric pre-concentrator. Appendix 3 provides a detailed description of the technique being utilised at Manchester for VOC analysis. This technique provides multivariate data documenting differences in the chemical composition of the urinary volatiles that may contain volatile biomarkers for a condition. This allows screening of populations rapidly using chemometric data analysis, neural networks and receiver operator curves to distinguish one population from another, with receiver operating curves being used to measure the appropriate thresholds to be set to distinguish samples as having colon cancer, colorectal adenomas, inflammatory bowel disease or microscopic colitis. Unlike GCMS – this technique does not provide identities of individual biomarkers but considers the data derived from the entire complex mixture of volatile chemicals that are present in urine headspace.

A receiver characteristic curve (ROC) with an area under the curve (AUC) of 0.63 or greater will be applied for the detection of SBD (colon cancer, colorectal adenomas or, inflammatory bowel disease). The threshold for participants samples being defined as having SBD will be >0.63 (see Appendix D).

To determine the relationship to the stool test (which is a quantitative continuous variable) a canonical correlation test will be applied. The canonical correlation tool is often used in a multivariate analysis of correlation. Canonical is the statistical term for analysing latent variables (which are not directly observed) that represent multiple variables (which are directly observed). Canonical correlation analysis is the analysis of multiple-X multiple-Y correlation. The canonical correlation coefficient measures the strength of association between two canonical variates. Canonical correlation analysis is preferable in analysing the strength of association between two constructs. This is because it creates an internal structure containing different importance of single item scores that make up the overall score.

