#### 8.2.2 Primary outcome analysis

The primary outcome is diagnostic accuracy - sensitivity, specificity, NPV and PPV of the dual index test, FIT and VOC. A FIT result that is >10 µgHb/g faeces OR a VOC result with predicted probability >0.63 implies that the participant is defined as having SBD and need to be referred for colonoscopy. We will report 2x2 tables of test accuracy of the dual test by the reference standard (final report from the CTC or colonoscopy examination and confirmatory histology report of SBD which is either colon cancer, colorectal adenomas or inflammatory bowel disease), alongside summary measures of sensitivity, specificity, NPV and PPV, and their 95% confidence intervals. Confidence intervals for sensitivity and specificity estimates that are very close to 1.0 will be according to the Zhou-Li method and the intervals for NPV and PPV estimates that are very close to 1.0 will be according to the Bayesian method (38). These test accuracy estimates will be used in the economic model.

We will analyse the combined FIT+VOC test results as both parallel (results from both tests are interpreted in combination) and serial testing (VOC performed only if FIT negative, i.e. <10  $\mu$ gHb/g faeces). The "or" rule will be considered in the interpretation of both parallel and serial tests where the diagnosis is positive when either test is positive (FIT >10  $\mu$ gHb/g faeces and/or VOC predicted probability >0.63), and negative when both are negative (FIT <10  $\mu$ gHb/g faeces and VOC predicted probability <0.63). In the serial test, if the FIT is positive (FIT >10  $\mu$ gHb/g faeces) then the diagnosis is positive. Otherwise, use the result from VOC and if it is positive (VOC predicted probability >0.63) then the diagnosis is positive. If the VOC result is also negative then the diagnosis is negative. Mathematically, both methods would give the same diagnostic results but would make a difference in the economic model.

A 2x2 table of test accuracy for each individual index test by the reference test will also be presented. Sensitivity, specificity, PPV and NPV will also be presented with their 95% confidence intervals for FIT only and VOC only. Participants with missing data for either of the index tests (FIT or VOC) or the reference standard (colonoscopy) will be excluded from this analysis.

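### The primary VOC cut-off of 0.63 has no stated basis on the score scale, so the accuracy of the dual test at that cut-off is unknown and not tied to the assumed 0.97 sensitivity

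*Protocol*

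**What the plan says.** Section 8.2.2 (Primary outcome analysis) sets the positivity rule as FIT above 10 µgHb/g "OR a VOC result with predicted probability >0.63 implies that the participant is defined as having SBD". Section 7.4 gives the same figure per sample: "The threshold for participants samples being defined as having SBD will be >0.63 (see Appendix D". The sentence before it applies 0.63 to a different quantity, the area under the ROC curve: "AUC) of 0.63 or greater will be applied for the detection of SBD".

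Appendix D describes the VOC score as a neural-network output scaled from 0 to 1. It then summarises the earlier study. For colorectal cancer (CRC), urinary VOC "gave a sensitivity of 0.63 (95% CI: 0.46–0.79) and specificity of 0.63 (95% CI: 0.59–0.67". "The AUC was 0.67 (95% CI: 0.57–0.77". For high-risk and all adenomas, sensitivity was 0.93 and 0.91, with specificity 0.16 and 0.15. The conclusion drawn is: "These data give a guide for fixing a sensitivity threshold for the VOC analysis which we propose as a probability of" 0.63. Appendix D adds that the value is to be adjusted during the study to improve performance.

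Three other places bear on this:
- Section 8.1 assumes a dual-test sensitivity for SBD of at least 0.97.
- Section 8.2.3 searches combined FIT and VOC thresholds with VOC running only from 0.63 to 1.
- Section 8.3 describes the primary-outcome thresholds used in the economic model as pre-specified.

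**The concern.** A cut-off on a predicted probability has to be chosen on the scale of that probability. Sensitivity, specificity and AUC are properties of a test at a cut-off, or over all cut-offs; they are not values of the score. The earlier results quoted in Appendix D include no score cut-off, so nothing in the protocol says what sensitivity or specificity an output of 0.63 corresponds to.

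This matters because 0.63 is half of the primary positivity rule, and the resulting accuracy estimates go into the economic model. If dual sensitivity came out well below 0.97, the reader could not tell whether VOC carries little information or whether the cut-off was badly placed. If the value is changed while the study runs, the primary estimate also risks optimism from choosing the cut-off on the data used to evaluate it. The one analysis that searches combined thresholds cannot go below 0.63, so it cannot find a more sensitive VOC cut-off.

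**Working it through.** **The plan's own figure.** Section 8.1: 200 SBD cases / 0.19 = 1,052.6, so 1,053; 1,053 / 0.55 = 1,914.5, so 1,915. The 95% interval width for 194/200 is 0.050 (Wilson), matching the stated 0.05. The sample size reproduces and is not affected by this point.

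**Where 0.63 could come from.** Section 1.9 reports 7 FIT-negative cancers, and FIT sensitivity was 0.80. That implies 7 / 0.20 = 35 cancers. Then 22/35 = 0.629, Wald 95% CI 0.47 to 0.79, close to the stated VOC sensitivity of 0.63 (0.46 to 0.79). So 0.63 behaves as an observed proportion of cancers detected.

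**What an output above 0.63 could mean.** Inputs:
- AUC 0.67 (Appendix D; a CRC figure, applied here to SBD).
- FIT sensitivity for SBD 1 − 0.37 = 0.63 (section 1.9, Dual Testing: 37% of SBD is FIT negative). Its equality with the cut-off is a coincidence.
- FIT specificity 0.93 (Appendix D, CRC).

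Assumptions: equal-variance normal scores; FIT and VOC independent given disease; outputs calibrated to the share of cases π in the training data. The protocol does not give π, so it is varied.

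Formulae:
- d = √2 × Φ⁻¹(0.67) = 0.622.
- Likelihood ratio at the cut-off: LR = (0.63/0.37) / (π/(1−π)).
- Score cut-off: t = d/2 + ln(LR)/d.
- VOC sensitivity = 1 − Φ(t − d); VOC specificity = Φ(t).
- Dual sensitivity = 0.63 + 0.37 × VOC sensitivity.

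| Case share π | VOC sensitivity | VOC specificity | Dual sensitivity, AUC 0.67 | Dual sensitivity, AUC 0.57 / 0.77 |
|---|---|---|---|---|
| 0.19 | 0.002 | 1.00 | 0.63 | 0.63 / 0.66 |
| 0.50 | 0.29 | 0.88 | 0.74 | 0.64 / 0.82 |
| 0.70 | 0.79 | 0.42 | 0.92 | 0.97 / 0.92 |

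The last column uses the limits of the AUC confidence interval.

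**If 0.63 happened to reproduce a reported operating point.**
- CRC point (0.63/0.63): dual sensitivity 0.63 + 0.37 × 0.63 = 0.86; dual specificity 0.93 × 0.63 = 0.59.
- High-risk adenoma point (0.93/0.16): 0.63 + 0.37 × 0.93 = 0.97; specificity 0.93 × 0.16 = 0.15.

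No text links either point to an output of 0.63.

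**What 0.97 would require in the same model.** VOC sensitivity among FIT-negative SBD must be (0.97 − 0.63)/0.37 = 0.919. Then t = 0.622 − Φ⁻¹(0.919) = −0.776 and VOC specificity is Φ(−0.776) = 0.22. The log likelihood ratio is 0.622 × (−0.776) − 0.622²/2 = −0.676, so LR = 0.51. The corresponding output is about 0.11 at π = 0.19, 0.34 at π = 0.50, and 0.54 at π = 0.70 (0.509 × 0.70/0.30 = 1.187; 1.187/2.187). All three lie below the floor of the combined search in section 8.2.3. They are illustrations, not proposed cut-offs.

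**The case against.** A reader might infer that 0.63 is a rule-in threshold at 19% prevalence, so that VOC will probably add little to FIT. The documents do not support that. It needs outputs calibrated to 19%, whereas Appendix D says only that outputs are scaled to 0 to 1 and that the network is trained on cases versus controls. With balanced training the modelled gain is 11 points (0.74 against 0.63). Section 1.9 also reports VOC sensitivities of 80%, 92% and 86% for cancer, adenomas and IBD, and detection of 6 of 7 FIT-negative cancers (exact 95% CI 0.42 to 1.00). These point to a useful gain, though they come without a score cut-off and so do not justify 0.63 either.

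A reader might also infer that the earlier sensitivity was simply relabelled as a probability. The protocol never says so; it is a strong inference, because no other basis is given. The AUC statement in section 7.4 could be meant as a minimum discrimination requirement, separate from the per-sample threshold. If so, the text should say that.

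The harm should not be overstated. Section 8.2.2 sets no pass or fail criterion and also reports VOC alone. Section 8.2.3 plots the individual VOC ROC curve with no stated floor, and section 8.3 takes both the primary and the optimised thresholds into the economic model. A badly placed cut-off would therefore be partly visible. That stands, but it does not give the primary rule a basis, and the combined search still starts at 0.63.

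**Conclusion.** The point holds in this form: the primary VOC cut-off has no stated basis on the network-output scale, and its accuracy is unknown. The illustrative model puts dual sensitivity for SBD at 0.63, 0.74 or 0.92 for training case shares of 0.19, 0.50 or 0.70, from no gain over FIT to a gain of 29 points. None of these shows a link to the 0.97 on which the design rests. The figures depend on binormal scores, conditional independence, a CRC-based AUC applied to SBD and an assumed case share. They show how wide the uncertainty is and do not predict the result.

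Two related faults are plain on the page. Appendix D allows the cut-off to move during the study, while section 8.3 treats the primary thresholds as pre-specified. And the combined search in section 8.2.3 excludes every VOC cut-off below the unsupported value.

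**What to change.** - In sections 7.4 and 8.2.2 and Appendix D, stop using 0.63 as both an AUC and a probability. If a minimum AUC is intended, state it separately with its own reason.
- Define the primary VOC cut-off on the network-output scale as the value that reaches a stated target sensitivity consistent with the 0.97 dual-test assumption. Give the reason for the target. Do not hard-code 92% or any numeric cut-off from the model above: the 92% rests on a single 37% estimate.
- Derive the cut-off only in development data, or in the training folds of participant-level cross-fitting, and lock it before the primary 2x2 table is computed. The protocol describes no earlier cohort on the same instrument, so cross-fitting may be the practical route.
- For the primary analysis, delete the Appendix D wording that lets the cut-off change during the study.
- In section 8.2.3, search VOC over the full 0 to 1 range.

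The cost is protocol text and programming, with no extra participants. The downside is specificity: at the modelled 0.97 point VOC specificity is about 0.22, which gives dual specificity of about 0.93 × 0.22 = 0.20 and leaves few investigations avoided. A more sensitive cut-off would also enlarge the CTC-negative, VOC-positive group that sections 6.4 and 6.6 expect to be small. Those sections must be reconciled with whatever threshold is chosen.
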